Communication is made entirely from incomplete expressions. It requires inference, questions and guessing by the listener. The flow of information can be exchanged, it is limited and the weight of the conversation falls on the listener.	1
The patient can, with the help of the examiner, have a conversation on familiar topics. There is frequent failure to express an idea, but the patient shares the weight of the conversation with the examiner.	2
The patient can deal with virtually all problems of daily living, with little or no help. However, reduced speech and/or comprehension make conversation on certain types of topics extremely difficult or impossible.	3
There is some obvious loss of speech fluency or ease of understanding with no significant limitation of the ideas delivered to their mode of expression.	4
Minimal observable impairments in speech. The patient may present subjective difficulties that are not evident to the listener.	5

Measurement scale. Quantitative, ordinal.

Patient satisfaction when performing rehabilitation therapy

Conceptual definition. Feeling of well-being or pleasure that one has when a desire has been fulfilled or a need covered. In relation to therapy, this feeling is linked to the development of different therapeutic activities ⁵⁰.

Operational definition. For this research, the Intrinsic Motivation Inventory will be used, which is a multidimensional measurement device designed to evaluate the subjective experience of the participants related to an objective activity in experiments; It consists of a varied number of subscale items, all of which have been shown to be factor analytically consistent and stable across a variety of tasks, conditions, and settings. The general criteria for the inclusion of items in the subscales have been a factor loading of at least 0.6 in the appropriate subscale. The multiple investigations in which they are used suggest that the order effects of item presentation appear to be negligible, and the inclusion or exclusion of specific subscales appears to have no impact on the others. Therefore, it is used as the equivalent of satisfaction, pleasure in carrying out the activity, and potential adherence to treatment. The Task Assessment version will be used, the subscales it includes are:

- Interest and satisfaction with the treatment
- Perception of competence (of the patient versus the treatment)
- Effort and importance of treatment
- Stress or tension (caused by the treatment)

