In each one, different questions are answered (Annex 2), and the answer is qualified from 1 to 7 points, where one is "not everything is true" and 7 is "very true".

Indicators. The sum of the scores obtained by the patient indicates that higher scores correspond to better states in the subject and are comparable between groups of participants or the same subject on different occasions.

Measurement scale. Qualitative, ordinal.

Demographic variables

Age

Conceptual definition. It is the time that a person has lived, counting from birth, measured in years ⁵¹.

Operational definition. For this study, the age reported by the patient measured in years or that found in the clinical record or any other legal document will be considered.

Indicators. The age reported by the patient or obtained from the clinical record or legal documents.

Measurement scale. Quantitative, ratio.

Sex

Conceptual definition. Set of anatomo-physiological characters that distinguish the male from the female among individuals of the same species ⁵¹.

Operational definition. What is referred by the patient or written in the clinical file or legal documents will be considered in this study.

Indicators. Referred by the patient or in the clinical record or legal documents.

- Women
- Man

Measurement scale. Qualitative, nominal, dichotomous.

SELECTION CRITERIA

Inclusion criteria

1. Adult patients between the ages of 35 and 70 with a clinically and tomographically proven diagnosis of a cerebral vascular event in the territory of the middle cerebral artery.
2. Patients with hemiparesis secondary to the cerebrovascular event
3. Patients with a maximum Ashworth of 2 and Brunnstrom of minimum 4
3. Patients with or without aphasia
4. Patients with a maximum evolution of 1 month from the start of the cerebrovascular event
5. Patients with a cerebrovascular event of either sex
6. Patients with a vascular event without cognitive deficit
7. Patients who agree to participate by signing an informed consent, by them or their family member or person in charge (Annex 3).

Exclusion Criteria.

1. Patients with uncontrolled comorbidities, such as arterial hypertension or diabetes mellitus, etc.
2. Patients with a known prior diagnosis of mental neurological disorder, such as dementia, psychiatric disorders, etc.
3. Patients with previous hemiparesis not fully recovered from any etiology.

Elimination criteria

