Minimal observable impairments in speech. The patient may present subjective difficulties that are not evident to the listener.	5

e) **Evaluation of satisfaction when performing rehabilitation therapy.** The characterization of the patient's perception of satisfaction will be evaluated by the same neuropsychologist, who will be blinded to the treatment the patient is receiving, using the Intrinsic Motivation Inventory (IMI). The IMI is a multidimensional measurement device intended to assess the subjective experience of participants related to an objective activity in experiments; it has been used in various experiments related to intrinsic motivation and self-regulation. The instrument assesses participants' interest/enjoyment, perceived competence, effort, value/utility, felt pressure and strain, and perceived choice while performing a given activity, yielding six subscale scores. The concepts of perceived choice and perceived competence are theorized to be positive predictors of both self-report and behavioral measures of intrinsic motivation, and pressure/strain is theorized to be a negative predictor of intrinsic motivation. Effort is a separate variable that is relevant to some motivation questions, so it is used as relevant. The value/utility subscale is used in internalization studies, with the idea that people internalize and self-regulate with regard to activities that they experience as useful or valuable to themselves.

The subscales and items are:

Intrinsic Motivation Inventory (Assessment of satisfaction when performing rehabilitation therapy)
 (Spanish versión)

	Reality Virtual			Restriction and Induction of Movement			TF and TO habitual		
Patient perception	Ini. Val.	Interm. Val.	Fin. Val.	Ini. Val.	Interm. Val.	Fin. Val.	Ini. Val.	Interm. Val.	Fin. Val.
Interest and satisfaction with treatment									
As he worked on the task he thought how much he enjoyed it.									
I found the task very interesting.									
Doing homework was fun.									
I really enjoyed doing homework.									
I thought the homework was very boring (R).									
I seemed the task very interesting.									
I would describe the task as very pleasant.									
Perception of competence (of the patient versus the treatment)									
I think I'm very good at this task.									
I think I did very well in this activity, compared with other									
I am satisfied with my performance in this task.									
I felt quite skilled at this task.									

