After working on this task for a while, I felt quite competent.									
Effort and importance of treatment									
I felt it was my choice to do the task.									
I didn't really have the option to do task (R).									
I felt like I was doing what I wanted to do while working on the assignment.									
I felt that I had obligation to do task (R)									
I did the homework because I had no other option (R).									
Stress or strain (caused by treatment)									
I didn't feel nervous about doing task (R).									
I felt tense while doing task.									
I felt relaxed while doing task (R).									
I was anxious while doing task.									
I felt stressed while doing task.									

Ini. Val.: initial valoration; Intermed. Val.: intermediate valoration; Fin. Val.: final valoration.

Subscale scores can be used as dependent variables, predictors, or mediators, depending on the research questions being addressed. The higher the score, the higher the satisfaction.

3. Therapy programs.

- a. Virtual reality program. The activities indicated in the tennis and ski software for the upper limb, covering cracks for both limbs and Star Wars-battles in the galaxy for the hand and fine pincer,

which will be carried out with the interface of the virtual reality equipment "connected" to the patient through movement sensors, with the multiperceptual feedback of the Kinect equipment or with googles.

b. *Movement restriction and induction therapy.* The patient will be placed a sling on the "healthy" thoracic limb, attached to the thorax, through a bra, gently but firmly, in such a way that it does not alter circulation or compress peripheral nerves. It will be explained to you that you should do all your activities with the "sick" member, to the extent possible. The restriction of the healthy side forces the patient to put all his effort into carrying out the activities of daily life, simulated during the therapy. This restriction will be carried out for 1 hour in therapy in the medical unit. And the patient will be told to repeat it at home at least once a day for one to five hours, without receiving support from family members while wearing the sling.

c. *Regular physical and occupational therapy.* The specific activities are shown in Annex 1. They include:

- **Motor management:** tasks to promote mobility of the shoulder, elbow, pentadigital clamp, fine clamp, transfers; volitional movements, eye-motor coordination, hip, knee, ankle and gait mobility.

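### The satisfaction score is read as higher = better, but the stress block of the Intrinsic Motivation Inventory is keyed so that higher means more tension

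*Combined protocol and SAP*

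**What the plan says.** The protocol measures satisfaction with the Intrinsic Motivation Inventory. Four subscales are listed under VARIABLES (Patient satisfaction when performing rehabilitation therapy), and stress or tension caused by treatment is the fourth. On scoring, that section says that "the answer is qualified from 1 to 7 points", with 7 meaning very true. Its Indicators paragraph adds: "The sum of the scores obtained by the patient indicates that higher scores correspond to better states in the subject", and treats the result as comparable between groups.

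Procedures, item 2 e), repeats the direction after the item list: "The higher the score, the higher the satisfaction". Just before that, it says subscale scores may serve as outcomes, predictors or mediators, depending on the question. Earlier in the same item it says that "pressure/strain is theorized to be a negative predictor of intrinsic motivation".

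The printed form (Procedures 2 e), repeated in Annex 2) has five stress items. The two calm ones, not nervous and relaxed, carry (R). The other three, including "I felt tense while doing task", do not. The documents do not say what (R) instructs the scorer to do.

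The Statistic analysis section names neither the Inventory nor a satisfaction score.

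**The concern.** A summed score can be read as higher = better only if every component points that way. In the interest block and the effort-and-importance block, (R) is on the unfavourably worded items, so reversal makes high mean favourable. In the stress block (R) is on the favourably worded items, so reversal makes high mean tense. The block is therefore keyed against the other three and against the stated rule. It also conflicts with the protocol's own account of strain as working against motivation.

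Secondary question 2 asks how satisfied patients are with their treatment, and question 3 relates satisfaction to adherence. If the arms differ in how tense they make patients, that difference would enter a total with the wrong sign.

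**Working it through.** The plan gives no range, cut-off or worked score for the Inventory, so there is no stated figure to reproduce. The check follows the printed items and the stated rule.

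**Inputs.** The form prints 7 interest, 5 competence, 5 effort-and-importance and 5 stress items: 7 + 5 + 5 + 5 = 22. Each is answered 1 to 7. Two things are assumed because the documents do not state them: that the sum runs over all 22 items, and that (R) means 8 − x. The second is varied below.

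**Range of a total.** Minimum 22 × 1 = 22, maximum 22 × 7 = 154, span 132. The stress block runs from 5 to 35, a span of 30, and 30/132 = 22.7%.

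**Stress block for two extreme patients.** In form order (not nervous, tense, relaxed, anxious, stressed), a fully calm patient answers 7, 1, 7, 1, 1 and a fully stressed one answers 1, 7, 1, 7, 7.

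- (R) as 8 − x: calm = 1 + 1 + 1 + 1 + 1 = 5; stressed = 7 + 7 + 7 + 7 + 7 = 35. Gap 30.
- (R) ignored: calm = 7 + 1 + 7 + 1 + 1 = 17; stressed = 1 + 7 + 1 + 7 + 7 = 23. Gap 6.
- (R) as 8 − x, then the block reversed as 40 − sum: calm = 35; stressed = 5.

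**Totals with the other 17 items at 4** (17 × 4 = 68):

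| Rule | Calm | Stressed | Stressed minus calm |
|---|---|---|---|
| (R) as 8 − x | 73 | 103 | +30 |
| (R) ignored | 85 | 91 | +6 |
| 8 − x, stress block reversed | 103 | 73 | −30 |

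With the other 17 items at their best (17 × 7 = 119), (R) as 8 − x gives the calm patient 119 + 5 = 124 and the stressed patient 119 + 35 = 154, the maximum possible. Ignoring (R) is no way out: the stress block still points the wrong way, and the effort-and-importance block inverts too (17 for the best answers, 23 for the worst).

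**When the other answers move as well.** Take (R) as 8 − x and a patient with two points more tension on each stress item. The block adds 2 × 5 = 10 points. If the same patient scores 10 points lower across the other 17 items (10/17 = 0.59 per item), the two cancel and the total shows no difference. With the block reversed, the same patient would total 10 + 10 = 20 points lower.

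**Subscales taken separately.** Nothing is then added with the wrong sign, but the stress subscale still runs from 5 (calm) to 35 (stressed) under (R) as 8 − x, so reading its high scores as a better state is still wrong.

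**The case against.** The strongest reply is that a 22-item total is an inference. The sentence about the sum follows a description of questions answered within each subscale. Procedures 2 e) describes the instrument as producing subscale scores and allows their separate use. This stands as far as it goes: under separate analysis the 30-point and 6-point gaps in a total do not arise. But the plan permits that analysis without committing to it, and the higher-is-better statement, made twice, exempts no subscale.

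The second reply is that the size depends on an undefined (R). That also stands, and the range of 6 to 30 points is given for that reason. The direction is wrong at both ends.

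A reader might go further and infer that more stressed patients, or a more stressful arm, will come out as more satisfied. The documents do not support that. The gaps hold with other answers equal, and the protocol itself expects strain to go with lower motivation. Since 17 of the 22 items lie outside the stress block, a diluted difference may be likelier than a reversed one. Nor can one say that the correlation with adherence will be pulled the wrong way. The Statistic analysis section specifies no such analysis, mentioning correlation tests only if potentially related variables are detected, and any distortion depends on how tension relates to adherence.

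Finally, the form records answers item by item, so the score can be corrected at analysis without loss.

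**Conclusion.** The scoring rule is wrong in direction for the stress block. This is an error as written rather than a missing detail, because following the stated rule gives a score that rises as the patient's state worsens. The conflict does not depend on how (R) is read, nor on whether the sum is taken over the whole form or within each subscale.

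The size is conditional. For a 22-item total with other answers equal, full stress against full calm adds 30 of 132 points if (R) is 8 − x, or 6 if (R) is ignored. For separate subscales, the error is confined to the interpretation of the stress score.

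The consequence is possible dilution or distortion of the between-arm satisfaction comparison and of its relation to adherence (secondary questions 2 and 3). Its direction and size in the trial cannot be predicted from the documents. The Fugl-Meyer hypothesis and the sample size are unaffected. The change should be made before satisfaction is analysed.

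**What to change.** Amend the Indicators paragraph, the closing lines of Procedures 2 e) and the Annex 2 form so that they agree:

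1. Define (R) as 8 − x for each marked item.
2. Choose one treatment of the stress block. Either enter it in the total as 40 minus its block sum (the same as 8 minus each of the five item scores after (R) is applied), or leave it out of the total and report it separately as lower = better.
3. State in the Statistic analysis section which score is the satisfaction outcome for secondary questions 2 and 3.

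Under the first option the total runs from 22 (worst on all four blocks) to 154 (best on all four), and higher = better becomes true. Under the second, the total covers 17 items and runs from 17 to 119. The cost is a few sentences in the scoring rule and a short recoding step at analysis. No new data, visits or patients are needed.

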Nevertheless, a meta-analysis (analysis of 40 reviews -19 Cochrane and 21 non-Cochrane-) mentions a moderate improvement with some techniques, including virtual reality; a "relative effectiveness" is described in relation to a small number of participants, as well as errors in the methodology (demographic variants, affected brain territory or severity of the condition, among others), inconsistency of results and little cost-benefit utility, suggesting the need to continue conducting studies ⁴¹. Another Cochrane review that included 37 trials and 1019 patients concluded that the evidence was low or very low, relating it to failures in the design of the interventions, the risk of bias could not be established because the studies were not clear, most of the participants were young and with more than one year since the EVC, in addition to the fact that some focus only on the upper limb (12 studies with 397 participants), finding that the differences were not significant for gait and global movement, but they were for the activities of daily living, so it is concluded that although the evidence suggests that virtual reality can be beneficial for the function of the upper limb and activities of daily life, there is still insufficient evidence on its effect on gait quality and global motor function. Nor can it be established yet which are the most important characteristics of virtual reality and what are its effects over time ⁴².

Clinical evaluation of patients with CVE

In patients with CVE and paresis of the extremities, different clinical scales are used to measure the changes that occur, spontaneously or related to rehabilitative management. There are multiple publications that support the relationship between the results of the Fugl-Meyer scale and the possible functionality of brain structures associated with movement. Cunningham described a good relationship ($rs = -0.768$; $p=0.016$; Spearman) between high scores with said scale and the functionality of the corticospinal tracts, preferably the contralateral ⁴³.

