Applied scales	Therapy whit virtual reality (n=13)	Therapy with restriction and induction of movement (n=23)	Occupational therapy alone (n=10)
Hand motor index	I.V. 20.77		20.20
	F.V. 24.92		22.80
	Diff. 4.15		2.6
Shoulder-elbow motor index	I.V. 41.15		37.20
	F.V. 47.85		44.0
	Diff. 6.7		6.8
Total motor index	I.V. 61.92		56.40
	F.V. 72.69		66.90
	Diff. 10.77		10.5
Fine Forceps Test	I.V. 4.30 ± 1.03	12 ± 4.99	3.90 ± 0.99
	F.V. 7.38 ± 1.19	17.34 ± 4.27	6.60 ± 0.96
	Diff. 3.007	5.34	2.8
Fugl-Meyer Scale	I.V. 28.31 ± 12.02	9.34 ± 3.7	27.70 ± 12.23
	F.V. 41.07 ± 9.28	11.27 ± 2.67	38.60 ± 11.8
	Diff. 12.77	1.93	10.9

V.I.: Initial Valoration V.F.: Final valoration Diff.: Difference.

JUSTIFICATION

Actually, the CVE continues to be one of the main causes of morbidity and mortality in Mexico and in the world; the neurological disability that it produces requires prolonged rehabilitation and the motor sequelae affect the quality of life of patients, due to gait problems, but above all hand problems. The lesions of the cortex in the affected territory during the CVE contribute to a deterioration of the corticospinal tract, and its Wallerian degeneration can spread over time if it is not stimulated, for this reason it is important to maintain the integrity and conservation of the corticospinal pathway. corticospinal tract, favoring motor recovery through therapy as soon as possible after the event was installed.

Despite the existence of multiple rehabilitation treatments for the motor disability of patients with CVE, the sequelae continue to maintain their proportion. Therapy supported by Virtual Reality and Modified Constraint-Induced Movement (TMIRm, by its acronym in spanish) are relatively recent, but have not yet been incorporated into the usual clinical application in our country. Various publications highlight that in the investigations there are methodological deficiencies, variations in the characteristics of the subjects, such as the territory affected or the time of evolution, for which reason the evidence is usually insufficient, especially its effect on the quality of gait and overall motor function. This work aims to solve the deficiencies of other publications and measure the influence of treatments early in patients after a CVE, which, in the future, could influence a better recovery, both in brain functionality and in its clinical representation, with minor sequelae.

RESEARCH QUESTION

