1. Clinical assessment and randomization. Once the patient, family member or person responsible has expressed their willingness to participate by signing the informed consent letter, they will be sent to office 16 of the outpatient rehabilitation clinic where they will be received by doctor 1 (treating) who will perform a clinical summary that will include age, sex, occupation, somatometry and the need for temporary incapacity for work, will carry out their own clinical evaluation in the way that is usually practiced in the office and will record it in the clinical file. He will be the one who monitors the patient as the treating physician and who answers all the questions that the patient, family member or person in charge may have throughout the investigation or in relation to his own condition, for which reason he will insist that he not give any information to the patient, doctor who will evaluate you later (evaluator 2) and who does not comment on aspects related to the therapy you are receiving, who reserves any doubt until the consultation. In addition, he will not know the results of the assessment using all the scales that the doctor will perform 2.

Finally, the investigator will write the corresponding information on the information capture sheet (Annex 4. Information collection sheet) and will randomly assign to the different therapeutic modalities by using a table of random numbers, which will be placed in the corresponding place of annex:

Group 1: Virtual reality

Group 2: Constraint-induced motion.

Group 3: Usual physical and occupational therapy.

When finished, the sheet will be sent to the responsible investigator, who will take the patient to physician 2 for the evaluation of the affected hemibody and date for language, then he will take him to the corresponding therapists to carry out the assigned treatment. An appointment will be made with the neuropsychologist for the evaluation of language and satisfaction.

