ANNEX 4.

INFORMATION COLLECTION SHEET

Folio No.: _____

Phone: _____ Address: _____

Name: _____ Affiliation: _____

Age: _____ Sex: _____ Treatment: _____ Date: _____

Diagnosis: _____

Type of CVE: _____ Ischemic: () Hemorrhagic: ()

Affected side: Right: () Left: ()

Clinical summary:

nPPA:

Alcoholism: Yes () No () Smoking: Yes () No ()

Schooling: Yes () No () Works: Yes () No ()

Specify: _____

Requires Disability: Yes () No () Specify: _____.

PPA: DM () HTA () Other: () Specify: _____.

Neurological diseases: Yes () No () Specify: _____.

Psychiatric illnesses: Yes () No () Specify: _____.

AP: _____

Physical exploration:

Treatment group: _____

Modified Ashworth scale

Segment	Ini. Val.	Interm. Val	Fin. Val.
Superior limb			
Lower limb			

Ini.Val.= Initial valoration;

Interm.Val.= Intermedia valoration;

Fin.Val.= Final valoration

Brunnstrom scale

Segment	Ini. Val.	Interm. Val	Fin. Val.
Superior limb			
Lower limb			

Ini.Val.= Initial valoration;

Interm.Val.= Intermedia valoration;

Fin.Val.= Final valoration

Appendix 1

TABLA 13.A. Tamaño de la muestra por grupo para comparar dos medias

α unilateral = α bilateral =	0,005			0,025			0,05		
	0,01	0,05	0,10	0,05	0,10	0,20	0,05	0,10	0,20
β = E/S*	0,05	0,10	0,20	0,05	0,10	0,20	0,05	0,10	0,20
0,10	3.563	2.977	2.337	2.599	2.102	1.570	2.165	1.713	1.237
0,15	1.584	1.323	1.038	1.155	934	698	962	762	550
0,20	891	744	584	650	526	393	541	428	309
0,25	570	476	374	416	336	251	346	274	198
0,30	396	331	260	289	234	174	241	190	137
0,40	223	186	146	162	131	98	135	107	77
0,50	143	119	93	104	84	63	87	69	49
0,60	99	83	65	72	58	44	60	48	34
0,70	73	61	48	53	43	32	44	35	25
0,80	56	47	36	41	33	25	34	27	19
0,90	44	37	29	32	26	19	27	21	15
1,00	36	30	23	26	21	16	22	17	12

* E/S es el tamaño estandarizado del efecto, calculado como E (tamaño esperado del efecto) dividido por S (desviación estándar de la variable de desenlace). Para estimar el tamaño de la muestra, se busca el tamaño estandarizado del efecto y se cruza el valor encontrado con los correspondientes a los valores especificados de α y β para hallar el tamaño requerido de la muestra en cada grupo.

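### Time since stroke at entry has no dedicated data field and no role in the between-group analysis, at a modest cost in precision

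*Combined protocol and SAP*

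**What the plan says.** - **Entry window.** The inclusion criteria admit "Patients with a maximum evolution of 1 month from the start of the cerebrovascular event". There is an upper bound and no lower bound.
- **Rationale.** The Justification attributes the weak evidence partly to "variations in the characteristics of the subjects, such as the territory affected or the time of evolution", then states: "This work aims to solve the deficiencies of other publications". The background section on clinical evaluation accepts that scores also change without treatment: "different clinical scales are used to measure the changes that occur, spontaneously or related to rehabilitative management".
- **Variables.** The Variables section defines the event, the three programmes, the motor, hand, language and satisfaction measures, age and sex. Time since stroke is not among them.
- **Data capture.** Under Procedures, item 1, the treating physician will "perform a clinical summary that will include age, sex, occupation, somatometry and the need for temporary incapacity for work". Annex 4 has one undefined date on the line "Age: _____ Sex: _____ Treatment: _____ Date", and tick boxes for stroke type and side ("Affected side: Right: () Left"). It has no field for onset date or days since stroke.
- **Allocation.** A table of random numbers is used. No stratification is stated.
- **Analysis.** The Statistic analysis section compares groups by repeated-measures ANOVA or Kruskal-Wallis and names no covariate. If a potentially related variable is detected, Pearson or Spearman correlations will be run.

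**The concern.** The onset date has to be known for every patient in order to apply the one-month limit, yet the plan does not then describe it or use it. If the six-week gain depends on how early in recovery a patient starts, entry day is a source of outcome variation. In arms of 17, chance differences in mean entry day would add noise to the virtual-reality-versus-usual contrast. The planned correlation test cannot remove that noise: it measures an association and leaves the group comparison unadjusted.

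There is also a reporting cost. The protocol sets out to study treatment given early and criticises earlier work for variation in time of evolution. Without a recorded value by arm, the report cannot show how early its patients were treated or how comparable the arms were on this point.

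**Working it through.** **Inputs from the documents**
- 17 evaluable patients per arm and SD 12.23 (Sample size).
- Pilot Fugl-Meyer changes of 12.77 (virtual reality) and 10.9 (occupational therapy), from Table 1. They differ by 1.87.
- Entry from onset up to one month.

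**Assumptions, because the documents are silent**
- Entry days are uniform over 0–30, 7–30 or 14–30.
- Recovery is exponential with time constant τ of 4 to 10 weeks.
- The mean six-week gain is 11 points, close to the pilot's 10.9.

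**1. The plan's own figure.** At a standardised effect of 1.00, one-sided α 0.05 and β 0.10, n = 2(1.645 + 1.282)² = 17.13. The appended table prints 17. The figure reproduces, and it makes no allowance for entry day.

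**2. Chance imbalance between two arms of 17.** The SD of a uniform variable is its width/√12. The SD of the difference in means is that value × √(2/17).

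| Entry window | SD of entry day | SD of difference in means | P(>3 days) | P(>5 days) |
|---|---|---|---|---|
| Days 0–30 | 8.66 | 2.97 | 31% | 9% |
| Days 7–30 | 6.64 | 2.28 | 19% | 3% |
| Days 14–30 | 4.62 | 1.58 | 6% | 0.2% |

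**3. Effect of a 3-day imbalance.** Expected gain is proportional to exp(−t/τ), so the shift is 11 × [1 − exp(−3/τ)], with τ in days.
- τ = 4 weeks (28 days): 11 × (1 − 0.898) = 1.12 points.
- τ = 10 weeks (70 days): 11 × (1 − 0.958) = 0.46 points.

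**4. Comparison with sampling error.** The SE of the difference is 12.23 × √(2/17) = 4.19 points. The shift is therefore 0.46/4.19 = 11% to 1.12/4.19 = 27% of one SE. Against the pilot difference of 1.87 it is 25% to 60%.

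**5. Share of variance, entry over days 0–30.** Near the mean, the slope is 11/τ points per day.
- τ = 28 days: 0.393 × 8.66 = 3.40 points; (3.40/12.23)² = 7.7%.
- τ = 70 days: 0.157 × 8.66 = 1.36 points; (1.36/12.23)² = 1.2%.

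**6. Gain in power at standardised effect 1, 17 per arm, one-sided 0.05.** Power = Φ[√(17/2)/√(1 − R²) − 1.645].
- Unadjusted: 89.8%.
- R² = 1.2%: 90.1%.
- R² = 7.7%: 91.8%.

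**The case against.** The strongest reply is that the protocol has already dealt with the variation it criticises. The Cochrane review in the background describes participants mostly more than one year after the event, and the title of the unit's own constraint-therapy pilot refers to subacute or chronic patients. Against that, a one-month cap and a single arterial territory are real design controls. This stands: only the variation within one month is at issue. A reader who sets the Justification beside the inclusion criterion might infer that the protocol repeats the fault it names, and the documents do not support that.

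A reader might also infer that the comparison is biased. It is not. Random allocation balances entry day in expectation, and the error rate of the unadjusted test already covers chance imbalance.

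Entry spread evenly from day 0 is also the case most favourable to the concern. Patients arrive by referral at an outpatient unit, need tomography and successive appointments, and must reach Brunnstrom 4. Very early starters are probably few, so the later windows in the table may be nearer the truth.

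Finally, recording is not excluded. The protocol asks for clinical data for the research file, Annex 4 has a free-text summary, and eligibility requires the timing. This stands in part: free text secures neither completeness nor use in the analysis.

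**Conclusion.** The point holds as a precision and reporting gap. Within the one-month window, time since stroke has no dedicated field and no part in the between-group comparison, although it must be known for eligibility and the protocol itself regards it as important.

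The size is modest. On the assumptions above, a 3-day imbalance moves the contrast by about 0.5–1.1 Fugl-Meyer points, against a standard error of about 4.2. Entry day over days 0–30 explains roughly 1–8% of variance, and adjustment raises power by about two percentage points at most. Later entry windows reduce both the imbalance and the gain. These figures rest on an assumed recovery curve and on SD 12.23, which in Table 1 is the SD of an initial score. The SD of change is not given; a smaller one would raise the share of variance explained.

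Set only against the pilot difference of 1.87, the shift can look decisive. Sampling error is the proper yardstick, and on that scale it is small. The change is worth making because it costs almost nothing.

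**What to change.** - **Record.** Add three dates to Annex 4: stroke onset, randomisation and first therapy session.
- **Define.** Add days from onset to randomisation to the Variables section.
- **Adjust.** Prespecify that variable, with baseline Fugl-Meyer, as covariates in an ANCOVA or equivalent linear model for the virtual-reality-versus-usual comparison. Kruskal-Wallis cannot carry a covariate, so the plan should say that this model is used whatever the Shapiro-Wilk result.
- **Do not adjust for days to first session.** That interval is fixed after allocation. The virtual-reality and constraint programmes run on different days from the other therapies, so the wait may differ by arm, and adjusting for it could distort the contrast.
- **Report.** Give days to randomisation and days to first session by arm.

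The cost is a few date fields, one of them already needed for eligibility, and one degree of freedom for entry day. No change to eligibility, treatment or sample size is needed.
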